2.1 Preparation, organization and management of this exploratory study

Part 1: Serial sampling of symptomatic and confirmed positive patients

Patients will be informed about the study by a health care worker at a non-ICU unit (“rampen unit”) of the University Hospitals Leuven, Belgium.

In case a candidate is interested in participating and tested positive for SARS-nCoV-2 on his/her nasopharyngeal swab, he/she will be informed about the study goals by the same health care worker. The volunteer will receive an information letter and a copy of the informed consent to take home.

Study procedure

After signing the informed consent, each patient will be asked to fill in a questionnaire (cfr. *Addendum A*).

The simplicity of performing a conjunctival swab makes it possible **to implement in the daily routine** of health care workers, **avoiding additional waste of personal protective equipment.**

Conjunctival sampling will be performed on both eyes after the application of a drop of topical anesthesia (Minims® Oxybuprocaine Hydrochloride 0.4%, Bausch and Lomb, Aubenas, Frankrijk). A timed 5 minutes will be in between application of the drop and the sampling. The sampling will be performed by a trained nurse and/or medical student and/or resident after proper training of correct sampling (cfr *Addendum B*).

Each eye will be sampled with a single, sterile, nylon, flocked swab (FLOQSwabs®; Copan, Brescia, Italy). This FLOQSwabs® is a **different** swab than the one used for routine nasopharynx SARS-nCoV-2 testing.

The sampling will be done from the nasal to temporal inferior conjunctival sac, the swab will be swirled in the opposite direction of the sampling itself.

The swabs will be placed in a tube with universal transport medium (UTM) and transferred to a -80°C freezer until further processing.

The conjunctival swab will be tested for SARS-nCoV-2 presence by making use of in-house reverse transcription real-time polymerase chain reaction (RT-PCR) designed for routine diagnostics targeting specific SARS-nCoV-2 genes in the clinical laboratory of the University Hospitals Leuven or at the REGA institute (laboratory of [name]).

Tear film SARS-nCoV-2 detection in symptomatic and pauci-symptomatic patients.

Serial sampling

Sampling will be repeated every 3 days to evaluate if PCR becomes positive during the course of disease and to monitor the duration of detectability of the virus in tears.

Part 2: Single sampling of pauci – symptomatic patients

Emergency patients, health care workers and patients hospitalized for a different condition/reason with a limited amount of symptoms (cfr. Inclusion criteria) that apply for a nasopharyngeal swab to confirm COVID-19 will be informed about the study by a pre-indicated health care worker.

When the patient is interested in participating he/she will be informed about the study goals by the same health care worker. The volunteer will receive an information letter and a copy of the informed consent to take home.

After signing the informed consent, each patient will be asked to fill in a questionnaire (cfr. *Addendum A*).

Study procedure

The conjunctival swabbing has been explained in detail in part 1.

3. Selection and withdrawal of subjects

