3.1 Inclusion criteria

- Subject needs to be above 18 years old.
- The subject is willing to undergo sampling of the conjunctiva.
- The subject is willing to fill in a questionnaire.
- The subject is fluent in written and verbal Dutch.
- The subject is capable of giving informed consent.
- Applicable for part 1 only: the subject test positive for SARS-nCoV-2 on a nasopharyngeal swab. The time window between a positive nasopharyngeal swab and the first conjunctival swab may be no more than 3 days.
- Applicable for part 2 only: mild symptoms of COVID-19 including symptoms of upper or lower respiratory tract infection and/or any body temperature elevation (criteria Sciensano for testing healthcare workers (April 12 2020)) without the need for hospitalization.

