Sampling with topical anesthesia can cause a transient stinging and blurring of the vision after instillation. When used in larger amounts, epitheliopathy of the cornea can be noticed. This is rare in the case of only one drop. Systemic absorption will be reduced by asking the patient to gently close the lids and to press on the medial canthus for a minute following the instillation of the drops. There are no known interactions with other medical products. It will not be used during pregnancy or lactation, nor will it be used in patients with a known hypersensitivity to the product.

After sampling the conjunctiva, there is a small possibility of a minor bleeding in the conjunctival sac which can induce a feeling of bruising of the tissue. Scarring due to the intervention is extremely rare (<0.01%).

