Hebt u de afgelopen dagen een verstopte neus ervaren?	Ja	Nee/...../.....
Moest u sinds kort meer en/ of heviger hoesten ?	Ja	Nee/...../.....
Bent u de afgelopen dagen kort van adem geweest?	Ja	Nee/...../.....
Hebt u pijn op de borst ervaren de voorgaande dagen?	Ja	Nee/...../.....

Tear film SARS-nCoV-2 detection in symptomatic and pauci-symptomatic patients.

Hebt u de afgelopen dagen koorts gemeten (een temperatuur boven de 38,5°)?	Ja	Nee/...../.....
Hebt u de afgelopen dagen spierpijnen ervaren?	Ja	Nee/...../.....
Hebt u de afgelopen dagen hoofdpijn ervaren?	Ja	Nee/...../.....
Hebt u de afgelopen dagen last gehad van diarree ?	Ja	Nee/...../.....
Hebt u de afgelopen dagen last gehad van buikpijnklachten ?	Ja	Nee/...../.....

Addendum B: Explanation of the sampling

1. Bij het afnemen van het staal draai je de borstel in de tegengestelde richting van de beweging. Voor het linker oog is dat tegenwijzerzin, voor het rechter oog is dat wijzerzin (geheugensteuntje: wrijven weg van de neus, draaien naar de neus)
2. Plaats de borstel in het universeel transport medium (UTM)
3. Plaats het UTM met staal in de koelkast op -18°C
4. Binnen de 24 u moet het UTM met staal verplaatst worden naar -80°C

De steriele wisscher openen aan de kant van de steel, dus weg van de borstel (vermijd direct contact met de borstel!).

De steriele wisscher vasthouden aan de steel, zo ver mogelijk van de borstel om bijbesmetting van de handen te vermijden.

De steriele wisscher vasthouden aan de steel, zo ver mogelijk van de borstel om bijbesmetting van de handen te vermijden.

Naar boven kijken en met de wijsvinger het onderooglid naar beneden trekken.
De borstel mag enkel de binnenkant van het ooglid aanraken, niet de buitenkant.

De borstel zacht glijden aan binnenkant ooglid van de neuskant naar de oorkant.
Draai de borstel in de tegengestelde richting, cf punt 4.

De borstel mag enkel de binnenkant van het ooglid aanraken, niet de buitenkant.
Houd bovendien ook afstand van de borstel.

[name]®

Na staalname de borstel onmiddellijk overbrengen naar de houder. Probeer aanraking met de borstel te allen tijde te vermijden!

Enkele cm's boven het borsteltje is er een rode verkleuring. Door deze op de rand van de houder te leggen, kan de borstel losgekraakt worden van de steel. de

[figure not shown]

Sluit onmiddellijk de houder en bewaar deze in de diepvries bij -20°C gedurende maximaal 2 dagen, nadien te bewaren op -80°C.

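### The patient presses beside the eye minutes before the tear swab with no clean hand or barrier required, so respiratory virus carried by hand could be scored as virus in tears

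*Combined protocol and SAP*

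**What the plan says.** Section 2.1 (Part 1, Study procedure) states: "Conjunctival sampling will be performed on both eyes after the application of a drop of topical anesthesia". On timing it adds: "A timed 5 minutes will be in between application of the drop and the sampling". On the path of the swab: "The sampling will be done from the nasal to temporal inferior conjunctival sac". Addendum B repeats the direction, from the nose side to the ear side: "De borstel zacht glijden aan binnenkant ooglid van de neuskant naar de oorkant". Part 2 refers back to Part 1 for the swabbing procedure.

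The pressing step stands only in Section 6, where it serves to limit systemic absorption of the anaesthetic. It consists of "asking the patient to gently close the lids and to press on the medial canthus for a minute following the instillation of the drops".

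Addendum B protects the swab in two ways. The stick is to be held "zo ver mogelijk van de borstel om bijbesmetting van de handen te vermijden", and contact is restricted to the inner side of the lid: "De borstel mag enkel de binnenkant van het ooglid aanraken, niet de buitenkant". It also has the lower lid pulled down with an index finger, without saying whose.

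For Part 1, Section 3.1 requires that "the subject test positive for SARS-nCoV-2 on a nasopharyngeal swab". Part 2 participants have mild COVID-19 symptoms and are already due for a nasopharyngeal swab.

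**The concern.** The people asked to press beside the eye are either known to carry the virus in the nasopharynx or are being tested because of symptoms. Their hands may carry respiratory secretions. The pressure is applied next to the sampling site, a few minutes before sampling, and nothing in the text requires the hand to be clean or covered. Material left at the canthus could enter the tear film once the eye opens and be picked up by the swab.

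Primary outcome 1 is presence of the virus in the tear film, so such a result would count as a positive. Hand carriage is also plausibly more common in people with a runny nose, cough or high nasal load. Contamination could then imitate the associations sought in primary outcome 2 (tear result and symptoms) and secondary outcome 5 (tear and nasopharyngeal results). In Part 1 the procedure recurs every three days, so a contaminated late swab could lengthen apparent shedding (secondary outcome 2).

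There is a second, simpler problem. Section 2.1 and Addendum B, the texts a sampler would work from, do not mention pressing. Some samplers may ask for it and others may not.

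**Working it through.** The plan gives no figure on this point to reproduce. The check sets the texts side by side and then illustrates the size under stated assumptions.

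**Timing.** Drop to swab is 5 minutes (Section 2.1) and pressure lasts 1 minute after instillation (Section 6). If pressing starts at instillation, it ends 5 − 1 = 4 minutes before the swab.

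**Place.** Pressure is at the medial canthus with the lids closed. The swab starts at the nasal end of the lower conjunctival sac, inside the lid. The two sites are adjacent but not identical.

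**Safeguards.** The documents contain no hand cleaning, tissue, glove or periocular cleaning step for the patient before pressing, and no control swab of skin or hands. The hand-contamination caution in Addendum B concerns holding the swab. The inside-of-lid rule is a partial barrier at the eye.

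**Later tests.** PCR-positive swabs go on to culture and subgenomic RNA testing (Section 1; secondary outcome 7). These address viability and replication. They do not show whether the material came from the eye or from the respiratory tract.

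**Size of the effect on positivity.** Let p be true tear positivity and c the chance that hand contamination turns a negative result positive. Both are assumed. Observed positivity = p + c(1 − p).

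| c | p = 5% | p = 2% |
|---|---|---|
| 0.1% | 5 + 0.1 × 0.95 = 5.095% | 2 + 0.1 × 0.98 = 2.098% |
| 1% | 5 + 1 × 0.95 = 5.95% | 2 + 1 × 0.98 = 2.98% |
| 2% | 5 + 2 × 0.95 = 6.90% | 2 + 2 × 0.98 = 3.96% |
| 5% | 5 + 5 × 0.95 = 9.75% | 2 + 5 × 0.98 = 6.90% |

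At p = 5%, the share of observed positives due to contamination runs from 0.095/5.095 = 1.9% to 4.75/9.75 = 49%.

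**Size of the effect on associations.** Assume p = 3% both with and without a runny nose, so the true odds ratio is 1, and let contamination differ between the two groups.

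- 4% v 1%: observed 3 + 4 × 0.97 = 6.88% and 3 + 1 × 0.97 = 3.97%; odds ratio (6.88/93.12)/(3.97/96.03) = 1.79.
- 2% v 1%: observed 4.94% and 3.97%; odds ratio (4.94/95.06)/(3.97/96.03) = 1.26.
- 0.4% v 0.1%: observed 3.388% and 3.097%; odds ratio (3.388/96.612)/(3.097/96.903) = 1.10.
- Equal contamination: odds ratio 1.

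**Serial sampling.** With three visits and independent contamination, the chance of at least one contaminated result is 1 − (1 − c)³. This is 0.3%, 3.0%, 5.9% and 14.3% for c = 0.1%, 1%, 2% and 5%.

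**The case against.** The strongest reply is that a false positive needs a chain of events: detectable virus on the hand, transfer to skin beside closed lids, movement into the sac, pick-up by a brush that may touch only the inner lid, and enough RNA for the PCR, with about four minutes between pressing and swabbing. Nothing in the documents gives a rate for that chain. Ill people also touch their eyes anyway, so the increment from this one step is unknown. Swabs are sterile and samplers are trained. The pictures in Addendum B are not available here, so any glove use they show cannot be checked. The study describes itself as exploratory and a pilot.

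Much of this stands, and it limits what can be claimed. It does not remove the route: closed lids protect only until the eye opens, and the inside-of-lid rule does not stop material that has already reached the tear film.

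A reader might infer several stronger things that the documents do not support:

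- That a finger is pressed exactly where the swab starts. Section 6 names no finger or tool, and the sites are only adjacent.
- That pressing precedes every swab. It stands in the safety section alone.
- That PCR's inability to separate live from dead virus creates the problem. That limit concerns viability, not origin.
- That the primary outcome is shown to be biased. Only a possible route is shown.

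**Conclusion.** The concern holds as a possible and avoidable source of false positives, not as a demonstrated bias. Followed as written, the pressing step brings a possibly contaminated hand beside the sampling site within the five minutes before sampling, without a hygiene requirement, and two of the three texts that describe the sampling leave the step out.

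The size cannot be derived from the documents. For assumed contamination of 0.1% to 5%, a true positivity of 5% would be observed as about 5.1% to 9.75%, which ranges from negligible to nearly double. The odds ratios shown depend wholly on the assumed difference in contamination between symptom groups and vanish if there is none. The direction for primary outcome 1 is towards false positives. A larger sample would not reduce the error, and the planned tests could not identify it afterwards. That justifies a cheap preventive step even if the true rate is low.

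**What to change.** - Make Section 2.1, Section 6 and Addendum B describe the same sampling steps, including the pressing step, so that it is done the same way each time.
- Add that the patient disinfects the hands before the drop and presses through a fresh clean tissue, a separate one for each eye.
- State in Addendum B who pulls down the lower lid, and that this is done with a clean or gloved hand. This contact is closer to the swab in time and place than the pressing.

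Having the sampler press with a fresh glove for each eye is not recommended. It would add contact and protective equipment, and the protocol gives limiting both as reasons for its sampling approach (Sections 1 and 2.1).

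The cost is hand gel, two tissues and a short time per sampling, plus a few lines of text. The safety purpose of the pressing step is left as it is.

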3.1 Inclusion criteria

- Subject needs to be above 18 years old.
- The subject is willing to undergo sampling of the conjunctiva.
- The subject is willing to fill in a questionnaire.
- The subject is fluent in written and verbal Dutch.
- The subject is capable of giving informed consent.
- Applicable for part 1 only: the subject test positive for SARS-nCoV-2 on a nasopharyngeal swab. The time window between a positive nasopharyngeal swab and the first conjunctival swab may be no more than 3 days.
- Applicable for part 2 only: mild symptoms of COVID-19 including symptoms of upper or lower respiratory tract infection and/or any body temperature elevation (criteria Sciensano for testing healthcare workers (April 12 2020)) without the need for hospitalization.

3.2 Exclusion criteria

- Allergy to Oxybuprocainehydrochloride
- Pregnancy or lactation

3.3 Expected duration of trial

Inclusion is planned between the end of April till the end of April 2021.

Tear film SARS-nCoV-2 detection in symptomatic and pauci-symptomatic patients.

4. Trial procedures

4.1 Summary of visits

Part 1: Serial sampling of symptomatic patients

Sampling will take place at the “rampen unit” of the University Hospitals Leuven, Belgium. Once the patient is admitted and tested positive for SARS-nCoV-2 on nasopharyngeal swab, conjunctival sampling will take place every three days until the day of discharge. The time window between a positive nasopharyngeal swab and the first conjunctival swab may be no more than 3 days.

Part 2: Single sampling of pauci-symptomatic patients

Sampling will take place at the emergency department of the University Hospitals Leuven, Belgium by the swab team. The sampling will not be repeated.

4.2 Supervision and responsibilities

The study will be performed under the supervision of dr. [name]. The subjects will be recruited at the equivalent of the former “rampen unit”, the emergency department and via a flyer (*cfr. Addendum C*) at several outpatient clinics of the University Hospitals Leuven, Belgium and by making an announcement on the intranet webpage of the University Hospitals Leuven, Belgium. The sampling of the conjunctiva will be performed by a trained nurse and/ or medical student and/or resident (*cfr. Addendum B*).

Volunteers will receive information about the study. Sampling will only occur upon written informed consent of the participants. The participating investigators will perform their part of the study fully in accordance with the terms of the Protocol, the applicable national and international laws (amongst others: the European General Data Protection Regulation of May 25, 2018) and apply and adhere to regulations and rules as, amongst others, the Declaration of Helsinki (2008) and ICH GCP Guidelines. Prof. [name] is assigned as a free of charge consulting sub-investigator without the power to recruit patients.

Insurance

In accordance with the Belgian Law relating to experiments on human persons dated May 7, 2004, UZ/KU Leuven shall assume, even without fault, the responsibility of any damages incurred by a Study Patient from the UZ/KU Leuven site and linked directly or indirectly to the participation to the Study, and shall provide compensation therefore through their insurance (Amlin Corporate Insurance, polisnr. 299.053.700, Vanbreda Risk & Benefits, [name]).

Informed consent

The Participating Site acknowledges that the Study can and will be conducted only on the basis of prior informed consent by the Subjects to participate in the Study. The Participating Site shall obtain a signed informed consent form (ICF) for all patients prior to their enrollment and participation in the Study in compliance with all applicable laws, regulations and the approval of the local Ethics Committee, if required. The Participating Site shall retain such ICFs in accordance with the requirements of all applicable regulatory agencies and laws.

5. Assessment of efficacy

Not applicable.

6. Assessment of safety

Sampling with topical anesthesia can cause a transient stinging and blurring of the vision after instillation. When used in larger amounts, epitheliopathy of the cornea can be noticed. This is rare in the case of only one drop. Systemic absorption will be reduced by asking the patient to gently close the lids and to press on the medial canthus for a minute following the instillation of the drops. There are no known interactions with other medical products. It will not be used during pregnancy or lactation, nor will it be used in patients with a known hypersensitivity to the product.

After sampling the conjunctiva, there is a small possibility of a minor bleeding in the conjunctival sac which can induce a feeling of bruising of the tissue. Scarring due to the intervention is extremely rare (<0.01%).

6.1 Recording of adverse events

The risks associated with the study-specific intervention, i.c. the conjunctival sampling and the use of topical anesthesia are listed above (*6. Assessment of safety*).

The participant will be asked to report any adverse event related to the study-specific intervention to the study team. These reported events will be documented by the Investigator in the source documents.

The following minimum information should be recorded for each adverse reaction:

- Adverse event description
- Start and stop date of the adverse reaction
- Severity

Tear film SARS-nCoV-2 detection in symptomatic and pauci-symptomatic patients.

- Seriousness
- Causality assessment to the study interventions
- Outcome

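### Section 6.1 leaves the first judgement of relatedness to the patient, and Part 1 repeats the drop and swab with no eye question tied to a repeat session: a minor gap that is cheap to close

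*Combined protocol and SAP*

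**What the plan says.** The rule for collecting adverse events is in section 6.1: "The participant will be asked to report any adverse event related to the study-specific intervention to the study team". The investigator then documents the events so reported. The minimum record for each one includes "Causality assessment to the study interventions".

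In Part 1, section 4.1 states that "conjunctival sampling will take place every three days until the day of discharge", and on the start it says: "The time window between a positive nasopharyngeal swab and the first conjunctival swab may be no more than 3 days". Section 2.1 describes each session: both eyes, an anaesthetic drop, a timed five-minute wait, then the swab. The sampler may be a trained nurse, medical student or resident. In Part 2, section 4.1 says: "The sampling will not be repeated".

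Section 6 gives the expected reactions. On the drop: "Sampling with topical anesthesia can cause a transient stinging and blurring of the vision after instillation", and with larger amounts "epitheliopathy of the cornea can be noticed. This is rare in the case of only one drop". On the swab: "there is a small possibility of a minor bleeding in the conjunctival sac which can induce a feeling of bruising of the tissue". It adds scarring, which it calls extremely rare.

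Section 1 raises eye pain as a possible COVID-19 symptom, and section 7.2 includes conjunctivitis among the onset symptoms. Addendum A asks about four eye complaints with their onset dates. Section 2.1 has it completed after consent and mentions no repeat.

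**The concern.** The request covers only events that are already related to the procedure. The patient must therefore decide on relatedness before reporting, and the investigator's causality assessment sees only what passes that screen. The order would better be reversed, because relatedness is a judgement for the investigator.

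The screen matters more here than in most swab studies. Part 1 patients have a disease that the protocol itself links to eye complaints, and they have filled in a questionnaire that treats such complaints as symptoms. A patient with red or irritated eyes two days after a session could reasonably blame the infection. Under section 6.1 that complaint would not have to be reported, and it might not be known when the next drop and swab are given. What is at stake is a small part of participant safety, not a study result.

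**Working it through.** The plan states no figure on this point, so there is none to reproduce. The check has two parts.

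**Where reactions and disease symptoms overlap.** Section 6 lists five reactions. The comparison with the four eye items in Addendum A (redness, irritation or pain, tearing, purulent discharge) is my own reading.

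| Reaction in section 6 | Similar Addendum A eye item |
|---|---|
| Stinging | Irritation or pain |
| Blurred vision | None |
| Corneal epitheliopathy | None mapped |
| Minor bleeding with a bruised feeling | Redness |
| Scarring | None |

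The overlap is 2 of 5. Timing weakens it for stinging, which follows the drop at once. Confusion is more plausible for redness or irritation that persists after the session.

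**How many repeat sessions lack an eye question.** Length of stay is not in the documents, so it is assumed. Let L be the days from positive nasopharyngeal swab to discharge, and d the lag to the first conjunctival swab, 0 to 3 days (section 4.1). The text does not settle whether a swab falls on the discharge day itself, so both readings are shown.

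- Discharge-day swab included: sessions = floor((L − d)/3) + 1.
- Discharge-day swab excluded: sessions = floor((L − d − 1)/3) + 1 if L − d ≥ 1, otherwise 0.

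Example: L = 14 and d = 3 with the discharge day included gives floor(11/3) + 1 = 3 + 1 = 4.

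| L (assumed) | Included, d = 0, 1, 2, 3 | Excluded, d = 0, 1, 2, 3 | Sessions if sampled at least once | Repeats (sessions − 1) |
|---|---|---|---|---|
| 3 days | 2, 1, 1, 1 | 1, 1, 1, 0 | 1 to 2 | 0 to 1 |
| 7 days | 3, 3, 2, 2 | 3, 2, 2, 2 | 2 to 3 | 1 to 2 |
| 14 days | 5, 5, 5, 4 | 5, 5, 4, 4 | 4 to 5 | 3 to 4 |

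Part 2 has one session and no repeats. Sections 2.1, 4.1, 6 and 6.1 were read for an eye question, symptom check or examination attached to a repeat session, and none is described. The counts show how often the added question would be asked. They do not estimate risk.

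**The case against.** The best case for the plan is that collecting only related events is proportionate for a drop and a swab in an exploratory study, and that the listed reactions are mostly mild and transient. Several parts of that case stand.

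- A patient who feels stinging straight after a drop is unlikely to blame COVID-19.
- At each session the lower lid is pulled down and the conjunctival sac is swabbed, so the sampler may see persisting bleeding. The patient's report is therefore not the only possible route, although the protocol does not require such an observation to be recorded.
- Section 6.1 says participants will be asked, without saying when or how often. Asking at each session is compatible with that, and the information letter and consent form, which are not in this copy, may say more. The finding is therefore limited to the protocol text. Even a prompt at every session would, as worded, cover related events only.
- Section 6.2 requires a yearly overview of all serious adverse events, related or not. What remains uncovered is mild events.
- Stopping for an investigator before every drop could delay swabs in the patients with ocular symptoms, whom the study wants to compare with tear positivity. For that reason the fix does not make such a call mandatory.

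A reader might also infer that section 6 understates corneal risk because it speaks of one drop while Part 1 gives several. The documents do not support this. One drop is correct for each session, no epitheliopathy rate is given, and nothing shows that drops three days apart raise the risk.

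**Conclusion.** The point holds as a minor one, and acting on it is a cheap improvement. The patient screens for relatedness before the investigator does, in a population where eye complaints may be disease, and the protocol text ties no eye question to the repeat sessions. For assumed stays of 3 to 14 days this concerns 0 to 4 repeat sessions per sampled Part 1 patient.

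A reader might infer that reactions are being missed or that an outcome is biased. Neither is shown: the documents contain no event data, and no endpoint depends on section 6.1. The conclusion rests on the wording of 6.1, on the assumed lengths of stay for the counts, and on my own matching of reactions to questionnaire items.

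**What to change.** In section 6.1, for both parts, ask participants to report any new or worsened eye complaint after sampling, regardless of cause, with causality judged by the investigator. The present request can stay for events outside the eye. This wording also reaches Part 2, single-session Part 1 patients and the period after a patient's last session, which a question at repeat sessions alone would miss.

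Add for Part 1: before each repeat drop, the sampler asks one short question about new or worsened redness, irritation or pain, tearing, discharge or blurred vision since the last session, without regard to cause. The answer goes into the source documents as safety data, separate from Addendum A. Sampling proceeds by default. The investigator is consulted before the drop only if the complaint began or worsened after the previous session and a reaction to the procedure is suspected. Any withheld swab is logged with its reason.

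The cost is a short paragraph in 6.1, a line on the source record and a log. At an assumed 1 minute per repeat session, the question takes 0 to 4 minutes per patient for stays of 3 to 14 days (0 to 4 repeats × 1 minute), not counting investigator calls. The downside is an occasional call, or a delayed or missed swab, in patients with ocular symptoms. Such gaps could be informative for the ocular-symptom and shedding-duration analyses; the default to proceed and the log limit this.
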